#### 1. Introduction

This study is a multisite, randomized, double-blind, placebo-controlled trial comparing efficacy and safety of prazosin versus placebo in AD patients with disruptive agitation either in long-term care or home-dwelling with a caregiver.

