#### 1.1 Randomization / Study Design

In this randomized, double-blind study design, eligible participants per site will be randomized using a 2:1 schedule to either the prazosin or placebo groups, and stratified by gender.

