#### 4. Efficacy Analysis

#### 4.1 Analysis of the Primary Outcome

Hypothesis 1a: Participants randomized to prazosin will manifest greater benefit on the primary outcome measure – the ADCS-Clinical Global Impression of Change in Agitation (ADCS-CGIC-A) anchored to disruptive agitation. The ADCS-CGIC-A is a 7-point scale that is structured as the clinician's assessment of change from baseline compared to the ADCS-CGIC-A Baseline Worksheet. A score of 1-2 indicates clinically meaningful improvement; a score of 3-5 indicates no clinically meaningful change; a score of 6-7 indicates clinically meaningful worsening.

The mITT data set will be used for primary analysis in this study. To address the aims for the primary efficacy analysis (Hypothesis 1a), longitudinal ADCS-CGIC-A scores from first post-baseline visit through 12 weeks will be analyzed using a mixed effects model for repeated measures (MMRM) to assess differences in ADCS-CGIC-A. The MMRM will include terms for time, intervention, intervention-by-time interaction plus covariates gender and severity of agitation at baseline defined as CMAI score. Time will be treated as categorical.

Differences in the primary outcome, ADCS-CGIC-A, between intervention groups will be tested at the two-sided 5% significance level. No adjustment to the type 1 error level will be made for secondary analyses.

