#### 4.2 Analysis of Secondary Outcomes

Hypothesis 1b: Participants randomized to prazosin will manifest greater benefit on the key secondary outcome measure – the Neuropsychiatric Inventory (NPI)/Neuropsychiatry Inventory-Nursing Home version (NPI-NH). Similar analyses to that described for the primary analysis will be performed on the total scores of the NPI/NPI-NH. An MMRM analysis as described above for the primary outcome measure will compare prazosin vs placebo at 12 weeks.

Hypothesis 1c: Participants randomized to prazosin will receive a lower cumulative total dose of lorazepam "rescue medication" administered during the trial. Similar analyses to that described for the primary analysis will be performed on the total dose of rescue lorazepam. Multiple linear regression

analysis will compare prazosin vs placebo through at 12 weeks. Gender and severity of agitation at baseline as measured by the CMAI will be included as covariates.

Hypothesis 1d: Study discontinuation ("dropout") due to persistent or worsening intolerable disruptive agitation will occur sooner in the placebo group than in the prazosin group. A Cox proportional hazards model will be used to compare the median time to dropout between groups adjusting for covariates (i.e., gender and baseline CMAI score). Those individuals who dropout for drug intolerance will be censored within this analysis according to their time from randomization to their last observation on protocol.

Hypothesis 1e: There will be larger proportion of responders to prazosin (defined as moderate or marked improvement) vs non-responders (defined as minimal improvement; no change; or minimal, moderate, or marked worsening) on the ADCS-CGIC-A. A logistic regression model including covariates of gender and baseline severity on CMAI will be used to compare percent of responders (ADCS-CGIC-A scores of 1 and 2) vs minimal or no change (ADCS-CGIC-A scores of 3, 4, and 5) vs worsening (ADCS-CGIC-A scores of 6 and 7).

Hypothesis 2: Participants randomized to prazosin will manifest greater benefit on the modified ADCS-Activities of Daily Living-Severe Dementia version (ADCS-ADL-Severe). Similar analyses to that described for the primary analysis will be performed on the ADCS-ADL-Severe. An MMRM analysis using the model specified for the primary outcome measure above will compare prazosin vs placebo at 12 weeks.

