Hypothesis 3: Participants randomized to prazosin will have a greater reduction in the NPI/NPI-NH "caregiver distress"/ "occupational disruptiveness" score. Similar analyses to that described for the primary analysis will be performed on the NPI/NPI-NH "caregiver distress"/ "occupational disruptiveness" score. An MMRM analysis using the model specified for the primary outcome measure above will compare prazosin vs placebo at 12 weeks.

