#### 4.3 Analysis of Exploratory Outcomes

Hypothesis 4: Participants randomized to prazosin will manifest greater benefit on the CMAI. Similar analyses to that described for the primary analysis will be performed on the CMAI. An MMRM analysis including gender as a covariate will compare prazosin vs placebo at 12 weeks.

Hypothesis 5: Improvement in the five domain NPI/NPI-NH subset score (Agitation/Aggression, Anxiety, Disinhibition, Irritability/Lability, and Aberrant Motor Behavior) will have a greater effect size in response to prazosin treatment than the 12-domain NPI/NPI-NH total score. An MMRM analysis using the model specified for the primary outcome measure above will compare prazosin vs placebo at 12 weeks.

Hypothesis 6: Participants randomized to prazosin will manifest greater improvement in sleep continuity during the 12-hour nighttime period and at each week during the 12-week study duration. Improvement in the primary actigraphy outcome measures will be defined as a decrease in locomotor

activity as assessed by total activity counts over the 24-hour period, specifically a decrease in the 12-hour period from 6 PM to 6 AM for each week of the 12 weeks of the study.

Due to small numbers, individual activity count time series and collection procedures will be reviewed by the Peace-AD actigraphy team (Drs. [name] and [name], OHSU) for practicability and hypothesis generation. No efficacy analyses will be performed.

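### NPI and NPI-NH scores, including two differently named distress scales, are analysed as one outcome with no version or setting term: a small, cheaply avoided loss of precision and clarity in Hypotheses 1b, 3 and 5

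*SAP*

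**What the plan says.** SAP section 1 enrols patients "either in long-term care or home-dwelling with a caregiver". Section 1.1 fixes the allocation: "eligible participants per site will be randomized using a 2:1 schedule to either the prazosin or placebo groups, and stratified by gender". Setting is not a stratum.

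Three hypotheses use the NPI family:

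- **Hypothesis 1b** (key secondary, section 4.2): "Similar analyses to that described for the primary analysis will be performed on the total scores of the NPI/NPI-NH".
- **Hypothesis 3** (section 4.2): participants on prazosin "will have a greater reduction in the NPI/NPI-NH 'caregiver distress'/ 'occupational disruptiveness' score". The analysis is a single model: "An MMRM analysis using the model specified for the primary outcome measure above will compare prazosin vs placebo at 12 weeks".
- **Hypothesis 5** (section 4.3): the five-domain subset "will have a greater effect size in response to prazosin treatment than the 12-domain NPI/NPI-NH total score".

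All three borrow the model of section 4.1: "The MMRM will include terms for time, intervention, intervention-by-time interaction plus covariates gender and severity of agitation at baseline defined as CMAI score". The SAP has no term for instrument version, setting, site or the outcome's own baseline value. It describes no rescaling and no separate analysis by version.

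**The concern.** The section 4.1 model was written for the ADCS-CGIC-A, a single change rating. It is carried over unchanged to an outcome that comes in two versions. The SAP expands NPI-NH as the nursing-home version, so it is reasonable to infer that long-term-care participants are rated on it and home-dwelling participants on the NPI, though the SAP does not say so outright.

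If the two versions differ in the score that is modelled, that difference is unexplained variance. With raw scores it is a difference in level. With change scores a constant level difference cancels, and only a difference in change matters. In a given trial the same variance appears as a shift in the treatment estimate when the arms happen to differ in setting mix.

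Hypothesis 3 has a further problem of meaning. Its labels name two things, the distress of a caregiver and the disruption of someone's work, and a pooled mean difference across them is hard to interpret even when the arms are perfectly balanced. Hypothesis 5 compares effect sizes. If these are standardised by a pooled SD, between-version variance enters that SD directly.

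**Working it through.** **Anchor.** The SAP states no figure for version or setting, so there is none to reproduce on this point. The sample sizes below come from section 2, and the largest was checked first. At delta 0.71, 2:1 allocation, 80% power and two-sided 5%, controls = 1.5 × ((1.960 + 0.842)/0.71)² = 23.4, rounded up to 24. The total is 3 × 24 = 72, and 72/0.9 = 80, as stated.

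**Inputs**
- From SAP section 2: the pilot range of 25-80, and the splits 53:27 (N=80) and 27:13 (N=40).
- 17:8 for N=25 is a rounding of 2:1; the SAP gives no split at that size.
- Assumed: share in each setting q = 0.5; version difference D = 0.5 within-version SD, range 0.3-0.8; simple randomisation.

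**Step 1: standard error without a version term.** The factor is √(1 + q(1−q)D²).
- D = 0.3: √(1 + 0.25 × 0.09) = 1.011
- D = 0.5: √(1 + 0.25 × 0.25) = 1.031
- D = 0.8: √(1 + 0.25 × 0.64) = 1.077

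This is an increase of about 3%, range 1-8%.

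**Step 2: chance imbalance in setting.** The SD of the difference in setting share between arms is √(q(1−q)(1/n₁ + 1/n₂)). The shift in the treatment estimate is the imbalance times D.

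| N (split) | One-SD imbalance | Shift at D = 0.5 |
|---|---|---|
| 80 (53:27) | 0.118 (12 points) | 0.06 SD |
| 40 (27:13) | 0.169 (17 points) | 0.08 SD |
| 25 (17:8) | 0.214 (21 points) | 0.11 SD |

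**Step 3: these are one quantity, not two.** The variance of the shift is D²q(1−q)(1/n₁ + 1/n₂). Adding the within-version variance (1/n₁ + 1/n₂) gives (1/n₁ + 1/n₂)(1 + q(1−q)D²), whose square root carries exactly the factor of Step 1. At 53:27, 0.0559 + 0.0035 = 0.0594, and √(0.0594/0.0559) = 1.03.

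**Step 4: consequences.**
- Power at N=80, delta 0.71 (in within-version SD), D = 0.5, all 80 analysed: 82.0% without the term against about 84.3% with it (the lost degree of freedom ignored).
- Exact binomial probability of an imbalance of 20 points or more: 8% at 53:27, 39% at 17:8.
- Simulation of 40,000 trials at 53:27, t-test without a setting term, D = 0.5: type I error is 5.0% over all randomisations, and 6.8% among trials with an imbalance of at least 20 points.

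**The case against.** A reader might infer that pooling biases the treatment comparison. The SAP does not support that. Allocation is randomised, so over all randomisations the estimate is unbiased and type I error stays near 5%. Only the estimate given a particular imbalance shifts. Nor may lost precision and imbalance be presented as two separate harms, because Step 3 shows they are the same variance, already carried by the unadjusted standard error. These objections stand.

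Further points on the other side:

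- **Size.** Shifts of 0.06-0.11 SD are small beside the effects of 0.71-1.2 SD in section 2. At N=80 a large imbalance is uncommon. This stands.
- **Inputs.** The SAP gives neither the setting split nor a version difference. For the total and subset scores, section 4.3 refers to a single 12-domain total and a single five-domain subset covering both versions, which suggests parallel content. This stands, and makes the case weaker for Hypotheses 1b and 5 than for Hypothesis 3.
- **Change scores.** Hypothesis 3 speaks of reduction and Hypothesis 5 of improvement. If change is modelled, a constant level difference cancels and only a version difference in change remains. The SAP does not settle which is modelled.
- **Per-site randomisation.** If sites recruit mainly from one setting, imbalance would be smaller than simple randomisation implies. The SAP does not say whether they do. Without a site or version term, the model's standard error would not reflect that balance in any case.
- **Informants.** It is tempting to add that the two distress scales come from different informants. The SAP describes neither informants nor scoring, so its text supports only that two differently named scales are merged.

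None of this removes the core. The SAP itself writes out the model, so the absent version term is a choice it has made and not a detail left to the protocol.

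**Conclusion.** The point holds as a modest matter of precision and interpretability, strongest for Hypothesis 3, and not as a demonstrated bias. The standard error is about 3% larger than it need be (1-8%) under an assumed 50/50 setting split, simple randomisation and a 0.5 SD version difference (0.3-0.8) in whichever score is modelled. With a version difference of 0.25 SD the increase is under 1%, since √(1 + 0.25 × 0.0625) = 1.008. Severity is minor: the outcomes concerned are secondary and exploratory, the trial is now a pilot, and the ADCS-CGIC-A analysis is untouched.

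**What to change.** In sections 4.2 and 4.3, add instrument version (NPI or NPI-NH) as a fixed covariate to the MMRMs for Hypotheses 1b, 3 and 5. For Hypothesis 3, also report the caregiver distress and occupational disruptiveness results separately by version, as descriptive results. The second step is needed because a covariate removes only a mean shift and does not make the two scales one construct.

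The cost is one degree of freedom and one extra table; version should already be on record for every participant rated. Specifying it in advance also avoids a post hoc decision should setting turn out to be imbalanced.

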#### 4.3 Analysis of Exploratory Outcomes

Hypothesis 4: Participants randomized to prazosin will manifest greater benefit on the CMAI. Similar analyses to that described for the primary analysis will be performed on the CMAI. An MMRM analysis including gender as a covariate will compare prazosin vs placebo at 12 weeks.

Hypothesis 5: Improvement in the five domain NPI/NPI-NH subset score (Agitation/Aggression, Anxiety, Disinhibition, Irritability/Lability, and Aberrant Motor Behavior) will have a greater effect size in response to prazosin treatment than the 12-domain NPI/NPI-NH total score. An MMRM analysis using the model specified for the primary outcome measure above will compare prazosin vs placebo at 12 weeks.

Hypothesis 6: Participants randomized to prazosin will manifest greater improvement in sleep continuity during the 12-hour nighttime period and at each week during the 12-week study duration. Improvement in the primary actigraphy outcome measures will be defined as a decrease in locomotor

activity as assessed by total activity counts over the 24-hour period, specifically a decrease in the 12-hour period from 6 PM to 6 AM for each week of the 12 weeks of the study.

Due to small numbers, individual activity count time series and collection procedures will be reviewed by the Peace-AD actigraphy team (Drs. [name] and [name], OHSU) for practicability and hypothesis generation. No efficacy analyses will be performed.

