#### 2. Power and Sample Size Determination

Power calculations for PEACE-AD were based on two-sample t-tests. Sample sizes were initially estimated targeting a power=80%, assuming a 2-sided alpha=5%, a standardized effect size of .44 SDs, and a dropout rate of 10%. This is a reasonable estimate of attrition given the study population and the relatively short follow-up period. Based on these considerations, 186 total participants are required: 124 in the prazosin group, and 62 in the control group.

Following COVID-19 in March 2020, it became clear that it would not be possible to successfully recruit this sample size to this protocol. In turn, a decision was made to change the focus to being a pilot trial of between 25-80 participants, a target number that was considered feasible in the aftermath of the pandemic. The range of sample sizes were then considered as a function of the standardized effect size delta; for delta = .71 the required sample size is 80 (53 in the prazosin group, and 27 in the control group), for delta = .79 the required sample size is 65 (43 in the prazosin group, and 22 in the control group), for delta = .91 the required sample size is 50 (33 in the prazosin group, and 17 in the control group), for delta = 1.0 the required sample size is 40 (27 in the prazosin group, and 13 in the control group), for delta = 1.2 the required sample size is 30 (20 in the prazosin group, and 10 in the control group).

The statistical analyses at study conclusion will be based on longitudinal regression data analysis that is expected to increase statistical power over the initial estimates with two-sample t-tests.

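### Hypothesis 5 claims a larger effect size for the five-domain NPI score than for the 12-domain total, but the stated analysis does not compare the two effects (minor)

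*SAP*

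**What the plan says.** SAP section 4.3 lists Hypothesis 5 among the exploratory outcomes. It concerns a subset of five NPI/NPI-NH domains: agitation/aggression, anxiety, disinhibition, irritability/lability and aberrant motor behavior. The claim is that improvement on this subset "will have a greater effect size in response to prazosin treatment than the 12-domain NPI/NPI-NH total score". The analysis given for it is one sentence: "An MMRM analysis using the model specified for the primary outcome measure above will compare prazosin vs placebo at 12 weeks".

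The model referred to is in section 4.1: "The MMRM will include terms for time, intervention, intervention-by-time interaction plus covariates gender and severity of agitation at baseline defined as CMAI score". It has one outcome variable.

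The 12-domain total is handled in section 4.2 under Hypothesis 1b: "Similar analyses to that described for the primary analysis will be performed on the total scores of the NPI/NPI-NH". Nothing in that paragraph refers to the five-domain subset, and Hypothesis 5 does not refer back to the analysis under Hypothesis 1b.

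Two design facts set the scale. Participants are "randomized using a 2:1 schedule to either the prazosin or placebo groups" (section 1.1), and after March 2020 "a decision was made to change the focus to being a pilot trial of between 25-80 participants" (section 2).

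**The concern.** Hypotheses 2 and 3 use the same MMRM sentence, and there it fits, because each claims that prazosin does better than placebo on one measure. Hypothesis 5 claims something else: that one treatment effect is larger than another, in the same participants. Its target is a difference between two standardized effects, and an arm comparison on one score does not estimate that.

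Three things are missing. The SAP does not say how an effect size is formed, in particular which SD is the divisor. Without that, raw differences on a five-domain and a 12-domain score are not comparable, because the scales have different ranges. It names no estimate or interval for the difference. It gives no criterion for calling one effect greater. Because the five domains are part of the total, the two estimates are correlated, and two separately fitted MMRMs do not supply the covariance that a standard error for the difference needs.

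What is at stake is limited but real. A pilot can inform the choice of outcome for a later trial, and whether the subset is more sensitive than the total bears on that choice. An apparent advantage reported without an interval could be chance.

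**Working it through.** **Plan's own figure.** The SAP gives no figure for Hypothesis 5, so there is nothing to reproduce. The finding rests on the text; the arithmetic only shows its scale.

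**Step 1. Hypothesis against model.**

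| | Needed for Hypothesis 5 | Supplied by the SAP |
|---|---|---|
| Five-domain score | Standardized week-12 effect | Week-12 arm difference from an MMRM (4.3) |
| 12-domain total | Standardized week-12 effect | Week-12 arm difference from a separate MMRM (4.2, Hypothesis 1b) |
| Standardizing SD | Named, for both scores | Not stated |
| Difference between the effects | Estimate and interval | Not stated |
| Criterion for a greater effect | Stated | Not stated |

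The model terms (time, intervention, their interaction, gender, baseline CMAI) include no term that distinguishes the two scores, so the difference cannot come out of the model as specified.

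**Step 2. Inputs for the illustration.**
- From the SAP, section 2: 80 participants as 53:27; effect sizes 0.71 SD (pilot, N=80) and 0.44 SD (initial plan); dropout 10%. These effect sizes are not specific to the NPI.
- From the SAP, section 4.1: the two-sided 5% level, stated there for the primary outcome and borrowed here.
- Assumed: correlation r between the two scores of 0.7 to 0.9, and equal true standardized effects. The SAP gives neither.
- After 10% dropout: 53 × 0.9 = 47.7 and 27 × 0.9 = 24.3, taken as 48:24.

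**Step 3. Comparing point estimates.** With equal true effects, the five-domain estimate is the larger with probability 1/2 by symmetry, at any sample size.

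**Step 4. Only the five-domain score significant.** Treat the two test statistics as bivariate normal with correlation r and common mean d / √(1/48 + 1/24), where √(1/48 + 1/24) = 0.25.
- d = 0.71: mean 0.71 / 0.25 = 2.84
- d = 0.44: mean 0.44 / 0.25 = 1.76

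The probability wanted is P(five-domain statistic > 1.96 and total statistic ≤ 1.96).

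| r | d = 0.71 | d = 0.44 |
|---|---|---|
| 0.9 | 4.8% | 7.0% |
| 0.8 | 6.9% | 10.0% |
| 0.7 | 8.4% | 12.4% |

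Counting disagreement in either direction doubles these figures, but only this half bears on wrongly favouring the subset.

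**Step 5. Precision of the difference.** For two scores each scaled to SD 1, SE = √(2(1 − r)(1/n₁ + 1/n₂)), and the 95% half-width is 1.96 × SE. The formula treats the SDs as known.
- 48:24, r = 0.9: SE = √(0.2 × 0.0625) = 0.112; half-width 0.22 SD
- 48:24, r = 0.7: SE = √(0.6 × 0.0625) = 0.194; half-width 0.38 SD
- N=25 as about 17:8, with 10% dropout (15.3:7.2): half-width about 0.40 SD at r = 0.9 and 0.69 SD at r = 0.7

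**Step 6. Power of a direct test.** With full enrolment at 53:27, a true gap of 0.2 SD would be detected with power 19% (r = 0.7) to 47% (r = 0.9). At 20:10 the corresponding figures are 10% and 21%. Estimation is therefore more realistic than testing.

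**The case against.** The strongest reply is that both pieces exist. The same MMRM is applied to the total under Hypothesis 1b and to the subset under Hypothesis 5. Each yields an adjusted week-12 difference and model variances, so two standardized effects can be derived and set side by side. This stands. A reader might infer that the trial cannot answer Hypothesis 5 at all, and that goes too far: the plan leaves a descriptive comparison open but does not say how to make it.

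A reader might also infer that the analysts will declare the subset better because one p-value falls below 5% and the other does not. The SAP states no such procedure. The probabilities in step 4 show what that reading would cost if someone adopted it; they do not describe the plan.

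It also stands that the stakes are low. The hypothesis is exploratory and the study is a pilot. The sentence "will be tested at the two-sided 5% significance level" concerns the primary outcome, and no primary or secondary conclusion depends on Hypothesis 5. A rule that demands an interval excluding zero can look too confirmatory here, and bootstrap refits of two MMRMs may fail or behave poorly with about eight placebo participants. These points bear on severity and on the form of the remedy. They do not close the gap between the hypothesis and its analysis. Under Hypothesis 6 the SAP explicitly drops efficacy analysis because numbers are small; it says nothing similar for Hypothesis 5.

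**Conclusion.** The point holds as a minor one. Hypothesis 5 is a claim about the difference between two correlated effects, and the analysis assigned to it is an arm comparison on a single score. Following the plan as written gives no estimate or interval for that difference.

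The text comparison needs no assumptions. The size does: under equal true effects, r between 0.7 and 0.9, N=80 and 10% dropout, reliance on point estimates would favour the subset half the time, and reliance on significance alone would favour it in roughly 5-8% of trials (0.71 SD) or 7-12% (0.44 SD). The difference would be known only to within about ±0.22 to ±0.38 SD, and less precisely at smaller sample sizes. The trial's primary conclusion is unaffected.

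**What to change.** Choose one of two changes in section 4.3.

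1. **Keep the hypothesis and add its analysis.** For each score, define the standardized effect as the adjusted week-12 arm difference divided by a named SD, for example the pooled baseline SD of that score, signed so that positive means benefit. Report five-domain minus 12-domain with a 95% interval from a participant-level bootstrap, resampled within arm and refitting both MMRMs each time. If refits fail at the low end of the sample size, use a joint model of the two standardized scores. State that this is exploratory estimation, and that Hypothesis 5 is not described as supported unless the interval excludes zero on the side favouring the five-domain score.

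2. **Reword the hypothesis.** Make it a prazosin-versus-placebo comparison on the five-domain score, with both standardized effects shown descriptively and no claim that one is greater.

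The first costs a few sentences and a short program, and its interval will be wide and may well not support the claim. The second costs a sentence and gives up the comparative claim.
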